13.1.8.3. Phase 1 Study Stopping Rule

Dose Escalation can be stopped earlier by a joint decision from SDP Oncology and the Investigators during an SRC meeting, by considering the model estimations and a global assessment of the safety, PK, pharmacodynamics, and preliminary clinical data.

The following safety event will trigger a temporary suspension of patient enrollment to study treatment if the posterior probability of target toxicity at each dose level exceeds 50% and is the highest among potential dose levels.

Based on the safety review with the SRC, SDP Oncology will determine whether the study may continue (with or without a protocol amendment) or if it must be terminated.

13.1.8.4. Phase 1 DLT Analysis

The DLT will be summarized by dose level using DAS for patients in Phase 1. By-patient listing of the DLTs will also be provided.

13.1.9. Phase 2

Bayesian posterior probability of response rate will be estimated continuously. The study may be stopped early for futility ($\text{Prob}(\theta \leq 0.05) > 0.90$) or efficacy ($\text{Prob}(\theta \geq 0.2) > 0.80$) during the enrollments starting from 10 enrolled efficacy evaluable patients. Study will be considered to be successful if $\text{Prob}(\theta \geq 0.2) > 0.50$ at the final analysis ($N = \sim 60$).

13.1.9.1. Efficacy Analysis

13.1.9.1.1. Phase 1 Efficacy Analysis

Phase 1 efficacy endpoints will be analyzed using Phase 1 Efficacy Analysis Set.

Efficacy analysis at Phase 1 will be conducted using similar methods defined in Phase 2 portion unless otherwise specified (details in [Section 13.1.9.1.2](#)).

Overall survival for Phase 1 is defined as the time from the date of initial dosing at same dose level or one dose level lower than RP2D to the date of death. Patients without documentation of death at the time of analysis will be censored at the date last known to be alive. Overall survival will be analyzed based on Phase 1 SAS patients.

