6.2. Secondary Objectives and Endpoints

Secondary Objectives	Study Endpoints
To determine the effect of TP-0184 on the treatment and the hematologic improvement of anemia in terms of hemoglobin increase, reduction in RBC transfusions and RBC Transfusion-Free \geq 8 weeks	
Response rate based on composite response criteria:
 
Hemoglobin increase \geq 1.5 g/dL maintained for a consecutive period of 8 weeks with no transfusions
 
OR
 
Reduction in units of \geq 4 RBC transfusions / 8 weeks (consecutive) compared with the pretreatment transfusion number in previous 8 weeks
 
OR
 
Patients who are RBC transfusion-free over any consecutive 8-week (56-day) period

To determine the effect of TP-0184 on the treatment and the hematologic improvement of anemia in terms of hemoglobin increase, reduction in RBC transfusions and RBC Transfusion-Free \geq 12 weeks	Response rate based on composite response criteria: Hemoglobin increase \geq 1.5 g/dL maintained for a consecutive period of 12 weeks with no transfusions OR Reduction in units of \geq 4 RBC transfusions / 12 weeks (consecutive) compared with the pretreatment transfusion number in previous 12 weeks OR Patients who are RBC transfusion-free over any consecutive 12-week (84-day) period
To measure time to RBC transfusion-free period	Time from first dose of TP-0184 to the first onset of a transfusion-free period for consecutive 8 weeks
To assess median duration of hemoglobin response	Duration of hemoglobin increase \geq 1.5 g/dL maintained for a consecutive period of $>$ 8 weeks with no transfusions.
To assess median duration of reduction in RBC transfusions (4 units / 8 weeks)	Duration of reduction in units of \geq 4 RBC transfusions / 8 weeks (consecutive)
To assess median duration of RBC-transfusion-free period \geq 8 weeks	Duration of RBC transfusion-free period
To assess progression to AML	Proportion of patients progressing to AML, time to AML progression
To assess overall survival	Time from first dose of TP-0184 to death due to any cause
To establish the PK profile of single agent TP-0184	PK parameters of TP-0184 as single agent: C_{max} , C_{trough} , t_{max} , AUC , and possibly others
Phase 2	

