7.3. Treatment Assignment

7.3.1. Calculation of Dose

In Phase 1, all patients will receive the dose of TP-0184 according to the cohort in which they are enrolled ([Table 3](#)).

Table 3: Planned Dose Escalation Levels

Dose Level	Dose (Daily Schedule)
-1	10 mg
1	20 mg
2	40 mg
3	60 mg
4	90 mg
5	120 mg
6	160 mg
7	210 mg
8	270 mg

Note: An intermediate dose level between the planned dose levels may be explored. In addition, based on a safety evaluation during the escalation phase, additional dose schedules than those outlined in the table may be explored after discussion and concurrence with SRC members and SDP Oncology clinical team.

Intra-patient dose escalation is not permitted in this protocol.

In Phase 1 and 2, patients will be treated for 24 weeks (6 cycles) and based on assessment of response, continue to receive TP-0184 in the absence of MDS disease progression or until loss of hematological response or unacceptable toxicity.

Note: Loss of hematological response (lack of response or refractory to further treatment) will follow the guidelines for progression/relapse after hematological improvement by IWG Response Criteria for MDS 2006 ([Appendix 6](#)).

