7.4. Dose Adjustment Criteria

Dose adjustments may be permitted for patients who experience toxicities. These toxicities will be discussed by the Investigators and Medical Monitor to determine if it would be in the best interest of the patient to continue to receive a reduced dose of TP-0184. Dose adjustments due to study drug related non-hematologic or hematologic AE severity are described in [Table 4](#) and [Table 5](#), respectively.

Decisions to reinstate dosing following a toxicity for which drug was held will be determined by the Investigator and Medical Monitor. In patients who receive subsequent and/or multiple treatment cycles, the TP-0184 dose may be reduced by one dose level based on the observed AE that occurred during the preceding cycle.

If further significant AEs occur during one or more cycles at the new reduced dose level, an additional dose reduction may occur (this allows for two dose reductions) EXCEPT in the first dose cohort where only one dose reduction (-1) will be permitted. If non-hematologic AE(s) > Grade 3 occur at the -1 dose the patient may be discontinued from the study pending discussion with the Investigator and Medical Monitor.

In the Phase 1 portion of the study, no dose re-escalations will be allowed for any patient who had a previous dose reduction due to AEs.

The Phase 2 treatment dosing schedule will be determined by the SRC and SDP Oncology clinical team based on the recommended Phase 2 treatment dose, and the MTD or MAD from Phase 1 safety data.

Guidelines for dose adjustments of TP-0184 following Cycle 1 and resolution of a patient's non-hematologic AE(s) to \leq Grade 1 and/or hematologic AE(s) to baseline CTCAE Grade are provided in [Table 4](#) and [Table 5](#), respectively.

Table 4 Guide to TP-0184 Dose Adjustments Due to TP-0184 Related Non-Hematologic AE

Non-hematological AE Grade	Action Regarding TP-0184 Dosage
Grade 1 – non-hematologic	None - maintain current dose level
Grade 2 – non-hematologic	Results in dose delay until AE severity recovers to \leq Grade 1. The investigator has the option to reduce dose by 1 dose level within the current or at the next cycle (beyond cycle one) with agreement of the Medical Monitor
Grade 3 ^a – non-hematologic ^b	Hold, then reduce dose by 1 dose level upon recovery to \leq Grade 1 with agreement of the Medical Monitor.
Grade 4 – non-hematologic	Discontinue treatment.

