13.1.5. Analysis Datasets

The safety analysis set (SAS) is defined as all patients who receive at least one dose of study drug (TP-0184) and will be used for safety analysis and related time to event analyses if applicable.

The DLT analysis set (DAS) is defined as patients evaluable for the determination of dose escalation in Phase 1 who met either one of the following criteria:

1. Experienced a DLT during the first 28 days (the DLT evaluation period)
2. Completed the DLT evaluation period and received at least 80% of planned doses.

Patients who did not meet either of the above criteria are not evaluable for the dose escalation assessment and may be replaced as needed to permit dose escalation. The DAS will be used for DLT related analysis.

The efficacy evaluable analysis set (EAS) is defined as all patients who have baseline data of Hemoglobin value, number of transfusions received in previous 12 weeks before study treatment, have received at least 1 dose of TP-0184, and have at least 1 available post baseline response assessment as per the composite endpoint criteria. The EAS will be used for analyses of response rate and related efficacy analyses.

Pharmacokinetic evaluable analysis set is defined as all treated patients in the trial with sufficient and adequate PK sample data as determined by SDP Oncology.

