The K-M survival curve and K-M median (if estimable), along with 2-sided 95% CIs will be provided.

13.1.9.1.2.11. Overall Survival

Overall survival is defined as the time from the date of initial dosing at RP2D to the date of death. Patients without documentation of death at the time of analysis will be censored at the date last known to be alive. Overall survival will be analyzed based on SAS patients whose initial dosing is RP2D.

The KM survival curve and K-M median (if estimable), along with 2-sided 95% Cis will be provided.

13.1.9.1.2.12. Hematopoietic Stem Cell Transplant Analysis

Hematopoietic stem cell transplant (HSCT) patients are defined as patients achieving a hematologic response and an HSCT in EAS. Summary statistics of the proportion of

hematopoietic stem cell transplant patients will be estimated with 2-sided 95% exact binomial confidence intervals among hematologic response in EAS.

13.1.9.1.2.13. MRI Imaging Analysis

Summary statistics will be provided based on MRI quantitative results by cohort, study, and overall patients. By-patient listings will be provided.

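### Phase 1 overall survival is timed from dosing at the RP2D or one level lower but analysed in everyone dosed, and this conflicts with the first-dose origin in the endpoint tables

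*Protocol*

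**What the plan says.** Protocol Section 13.1.9.1.1 gives the Phase 1 OS interval as "the time from the date of initial dosing at same dose level or one dose level lower than RP2D to the date of death". It then names the population: "Overall survival will be analyzed based on Phase 1 SAS patients". Section 13.1.5 defines that safety set as "all patients who receive at least one dose of study drug (TP-0184)", with no condition on dose level.

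The endpoint tables define the same endpoint differently. The synopsis and Section 6.2 of the protocol, and Section 1.2 of the SAP, all give "Time from first dose of TP-0184 to death due to any cause".

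For Phase 2, Section 13.1.9.1.2 states its restriction openly: "Overall survival will be analyzed based on SAS patients whose initial dosing is RP2D".

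Three rules decide who can reach a given dose level:

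- Upward movement is barred: "Intra-patient dose escalation is not permitted in this protocol" (Section 7.3.1, Calculation of Dose).
- Downward movement is allowed. Under Section 7.4, "the TP-0184 dose may be reduced by one dose level based on the observed AE that occurred during the preceding cycle", and after further significant events "an additional dose reduction may occur (this allows for two dose reductions)". Table 5 also lowers the dose by one level after a rapid hemoglobin rise.
- Patients with a dose-limiting toxicity (DLT) in Cycle 1 leave the study (Section 7.4.2), so they are not reduced into a lower level.

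**The concern.** A time-to-event endpoint needs an origin for every patient in its analysis set. Here the origin exists only for patients dosed at one of two levels, while the set contains all levels. The programmer must drop patients silently, substitute another date, or use the endpoint-table definition, and each choice gives a different survival curve under the same name.

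A second problem appears if the words are taken literally. A patient who starts above the RP2D and is later reduced into it would have time zero at the reduction. The time already survived on treatment is then not counted, and the patient enters only by having survived to that date. Because a rapid hemoglobin rise is one reason to reduce, such entry could favour patients whose anemia is improving, while a patient with a Cycle 1 DLT above the RP2D never enters.

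The origin also depends on a dose chosen only after Phase 1 data are reviewed. If no RP2D is declared, nobody has a start date under this text.

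**Working it through.** The plan gives no figure that rests on the OS definition, so there is nothing to reproduce. The check has two parts.

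**1. Who has an origin under the literal text**

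| Starting level | Origin under Section 13.1.9.1.1 | Origin under Section 6.2 |
|---|---|---|
| Two or more below the RP2D | None, because escalation is barred | First dose |
| One below the RP2D | First dose | First dose |
| RP2D | First dose | First dose |
| Above the RP2D, not reduced into it | None | First dose |
| Above the RP2D, reduced into it | Date of reduction (literal reading) | First dose |

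The two definitions agree only in the second and third rows.

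**2. How many patients this could affect**

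Inputs from the protocol: eight planned levels from 20 to 270 mg (Table 3), about 1 to 6 patients per level (Section 7.1.1), at least 6 at the recommended dose (Appendix 2, stopping rules) and about 30 patients in Phase 1 (Section 7.2). The RP2D and the actual cohort sizes are unknown, so these are assumptions: 1, 3 or 6 patients per level, 6 at the RP2D, the RP2D at any of the eight levels, 0 to 2 levels explored above it, and nobody starting at 10 mg.

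Let e be the number starting at the RP2D or one level below, and N the number dosed. Judged by starting dose, the share with no origin is 1 − e/N.

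With 3 per level, 6 at the RP2D and nothing explored above it:

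- RP2D 20 or 40 mg: e = N, so 0%.
- RP2D 60 mg: e = 9, N = 12, so 3/12 = 25%.
- RP2D 90 mg: e = 9, N = 15, so 6/15 = 40%.
- RP2D 120 mg: e = 9, N = 18, so 9/18 = 50%.
- RP2D 270 mg: e = 9, N = 27, so 18/27 = 67%.

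Over the whole grid the share runs from 0% to 46% with 1 per level (6/13), to 67% with 3 per level (18/27) and to 75% with 6 per level (36/48). The last pattern exceeds the planned 30 patients. Fixing N = 30 instead, e = 12 gives 18/30 = 60%, e = 9 gives 21/30 = 70%, and the extreme e = 7 gives 23/30 = 77%.

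The cohort patterns in protocol Table 15 can be used in the same way, taking the recommended next dose as the RP2D and topping it up to 6. The last column assumes, as a limit, that every patient above the RP2D is reduced into it except the one with a DLT.

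| Scenario | RP2D | Patients by level | e/N | No origin by starting dose | No origin at the limit |
|---|---|---|---|---|---|
| 4 | 90 mg | 3, 3, 3, 6 | 9/15 | 6/15 = 40% | 6/15 = 40% (none above) |
| 5 | 90 mg | 3, 3, 3, 6, 4 | 9/19 | 10/19 = 53% | (10 − 3)/19 = 37% |
| 7 | 120 mg | 3, 3, 3, 3, 6, 4 | 9/22 | 13/22 = 59% | (13 − 3)/22 = 45% |
| 8 | 120 mg | 3, 3, 3, 3, 6, 6 | 9/24 | 15/24 = 62.5% | (15 − 5)/24 = 42% |

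Reductions therefore lower the share without an origin, but each patient gained this way (at most 3, 3 and 5 here) is a late starter.

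Table 14 cannot narrow the range. Its patients per toxicity band do not add up to its patients per trial: in scenario A, 0.3 + 10.3 + 0 = 10.6 against 21.3.

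**The case against.** The best defence is that the authors meant starting dose. Phase 2 OS is limited to patients whose initial dosing is the RP2D, and the SAP describes its Phase 1 fatigue analysis as a subgroup at the RP2D and one level below. On that reading the clock starts at first dose, nobody enters late, and only the restriction is missing. This is plausible, and it removes the late start. It does not rescue the section: the population sentence still names the unrestricted safety set, and the endpoint tables still apply to all Phase 1 patients.

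A reader might infer that most Phase 1 patients lack a start date. The documents do not support this as a general statement, because they fix neither the RP2D nor the cohort sizes. The inference is also sensitive to N: 12 patients in the two levels out of the 21.3 simulated on average in Table 14, scenario A, would leave 12/21.3 = 56% with an origin.

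A reader might also infer that survival is certainly biased by late entry. That needs the literal reading and patients who start above the RP2D, avoid a Cycle 1 DLT and are then reduced into it. The documents give no number of such patients.

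Finally, the usable definition already stands in Section 6.2 and the SAP, and no OS estimate is now planned. Both points are true. They limit the consequence but do not make Section 13.1.9.1.1 correct.

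**Conclusion.** The point holds as an internal contradiction that makes the Phase 1 OS definition wrong as written. The mismatch between origin and population, and the conflict with the endpoint tables, follow from the text alone and need no assumption about cohort sizes.

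The share of patients without an origin is path-dependent, from 0% to roughly three quarters under the assumptions above, and 40% to 62.5% by starting dose on the Table 15 patterns. The late start is conditional on the literal reading and cannot be sized from the documents.

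Severity is low. Phase 1 OS is a secondary endpoint, and no sample size, escalation rule or success criterion uses it. SAP Section 2 records termination with two patients and plans listings only.

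**What to change.** In Section 13.1.9.1.1, define Phase 1 OS from the first dose of TP-0184, at whatever level, for all Phase 1 safety-set patients, as Section 6.2 already does. If a summary near the RP2D is wanted, add it as a subgroup defined by starting dose: the RP2D or one level lower.

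Every patient in the set then has a start date (0% missing), no clock starts late, and the section agrees with the synopsis, Section 6.2 and the SAP. The subgroup would hold about 6 to 12 patients under the assumed cohort sizes (9 with 3 per level and 6 at the RP2D; 6 if the RP2D is the first level), so it would be descriptive only.

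The cost is one sentence, with no effect on sample size or data collection. Section 13.1 lets the SAP modify planned analyses, so the correction could sit there. With the trial terminated, it matters mainly if this text is reused.

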13.1.9.1.2. Phase 2 Efficacy Analysis

13.1.9.1.2.1. Response Rate

Response rate is defined as the proportion of patients who achieves response according to the composite endpoint criteria for a consecutive period of 8 weeks ([Appendix 1](#)). Response rate will be estimated with 2-sided 95% exact binomial confidence intervals based on EAS.

13.1.9.1.2.2.12-Week Response Rate

The 12-Week response rate is defined as the proportion of patients who achieves response according to the composite endpoint criteria for a consecutive period of 12 weeks ([Appendix 1](#)). The 12-Week response rate will be estimated with 2-sided 95% exact binomial confidence intervals based on the EAS.

13.1.9.1.2.3. Time to RBC transfusion-free analysis

Time to RBC transfusion-free period is defined as the time from the date of initial dosing at RP2D to first documentation of a transfusion-free period for patients who have one or more transfusion-free periods. Transfusion-free period is defined as the period that a patient becomes transfusion-free for consecutive 8 weeks or longer after treatment of TP-0184. Kaplan-Meier (K-M) survival curve and K-M median (estimate), along with 2-sided 95% CIs, will be provided.

13.1.9.1.2.4. Duration of Hemoglobin Response

Duration of hemoglobin response is defined as the time from the date of first documentation of a hemoglobin response to the date of first documentation of progression of hemoglobin response for hematologic responders. Hemoglobin response is defined as an increase ≥ 1.5 g/dL maintained for a consecutive period of > 8 weeks with no transfusions; hemoglobin progression is defined as a change from baseline < 1.5 g/dL of the hemoglobin or the start of one or more transfusions.

The K-M survival curve and K-M median (estimate), along with 2-sided 95% CIs will be provided.

13.1.9.1.2.5. Duration of Reduction in RBC Transfusion for 8 Weeks Analysis

High transfusion burden patient with reduction in RBC transfusion for 8 weeks is defined as high transfusion burden patients (baseline ≥ 4 U transfusions) patients with change from baseline of equal or more than 4 units transfusions in consecutive 8 weeks in EAS.

Duration of reduction in RBC transfusions for 8 weeks is defined as the time from the assessment date of consecutive 8 weeks with reduction from baseline of RBC transfusions ≥ 4 units to the assessment date of the reduction from baseline < 4 units or increased transfusions frequencies from baseline within a consecutive 8 weeks. For high transfusion burden patient with reduction in RBC transfusion.

The K-M survival curve and K-M median (estimate), along with 2-sided 95% CIs will be provided.

13.1.9.1.2.6. Duration of RBC Transfusion-Free Period ≥ 8 weeks

RBC transfusion-free period ≥ 8 weeks patient is defined as a patient who maintains RBC transfusion-free during consecutive 8 weeks or longer in EAS.

Duration of RBC transfusion-free period ≥ 8 weeks is defined as the time from the assessment date of consecutive 8 weeks without any RBC transfusions to the assessment date of the first documented transfusion in the following visits for RBC transfusion-free period ≥ 8 weeks patients.

The K-M survival curve and K-M median (estimate), along with 2-sided 95% CIs will be provided.

13.1.9.1.2.7. Changes in Neutrophil Count

Hematologic improvement in neutrophil count (HI-N) is defined as patients achieving over any consecutive 8-week (56-day) period and / or decrease in neutrophil levels in EAS.

Change in neutrophils analysis will provide summary statistics of the proportion of patients with hematologic improvement in neutrophil count with 2-sided 95% exact binomial confidence intervals using EAS.

13.1.9.1.2.8. Changes in Platelet Count

Hematologic improvement in platelet count (HI-P) is defined as patients achieving hematologic improvement in platelets over any consecutive 8-week (56-day) period and / or decrease in platelet levels in EAS.

Change in platelet count analysis will provide summary statistics of the proportion of patients with hematologic improvement in platelet count with 2-sided 95% exact binomial confidence intervals using EAS.

13.1.9.1.2.9. Progression to AML

Progression to AML is defined follow the guidelines by IWG Response Criteria for MDS 2006 ([Appendix 6](#)).

Summary statistics of the proportion of patients progressing to AML will be estimated with 2-sided 95% exact binomial confidence intervals based on EAS.

13.1.9.1.2.10. Time to Progression to AML

Time to progression to AML is defined as the time from the date of initial dosing at RP2D to the date of first documented progression to AML using EAS.

The K-M survival curve and K-M median (if estimable), along with 2-sided 95% CIs will be provided.

13.1.9.1.2.11. Overall Survival

Overall survival is defined as the time from the date of initial dosing at RP2D to the date of death. Patients without documentation of death at the time of analysis will be censored at the date last known to be alive. Overall survival will be analyzed based on SAS patients whose initial dosing is RP2D.

The KM survival curve and K-M median (if estimable), along with 2-sided 95% Cis will be provided.

13.1.9.1.2.12. Hematopoietic Stem Cell Transplant Analysis

Hematopoietic stem cell transplant (HSCT) patients are defined as patients achieving a hematologic response and an HSCT in EAS. Summary statistics of the proportion of

hematopoietic stem cell transplant patients will be estimated with 2-sided 95% exact binomial confidence intervals among hematologic response in EAS.

13.1.9.1.2.13. MRI Imaging Analysis

Summary statistics will be provided based on MRI quantitative results by cohort, study, and overall patients. By-patient listings will be provided.

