25. Live vaccines within 14 days prior to first study drug administration. COVID-19 vaccines (non-live) approved by regional health authorities are allowed.
26. Medications that are known strong to moderate CYP3A4 inducers must be discontinued at least 21 days prior to first dose of study drug. Medications that are known strong to moderate CYP3A4 inhibitors must be stopped 21 days (or 5 half-lives, whichever is shorter) prior to the first dose of study drug.
27. Patients who have received medications with known or possible risk of prolonging the QT interval or inducing Torsades de Pointes within the previous 7 days.

Investigational product, dosage, schedule and mode of administration:

TP-0184, administered orally once a day, taken in the morning after an overnight fast (minimum of 6 hours) with up to 200 mL or 7 ounces of water. Study participants should wait at least 1 hour before ingesting any food, liquid (other than water), or other medications.

Duration of treatment:

The expected duration of treatment will be for 24 weeks (6 cycles). Furthermore, based on assessment of response, patients may continue to receive TP-0184 in the absence of MDS disease progression or until loss of hematological response or unacceptable toxicity.

Statistical methods:**Phase 1**

Two-parameter BLRM with EWOC will be used to guide dose escalation and estimate the MTD based on occurrence of DLT during Cycle 1. The MTD with estimated posterior probability of a DLT within target toxicity interval (16%, 33%) among the admissible doses fulfilling EWOC is determined by BLRM. MTD is estimated based on observed DLTs.

After completing a given dose escalation cohort, the decision to move up to a planned cohort or not, or to adjust to a lower or slightly higher dose, will be assessed based on BLRM with EWOC and integrate all available safety data, PK and other clinical data using the BLRM method as guidance for dose escalation. A SRC will consist of the Principal Investigators, an independent cardiologist, the Safety Lead, the Statistician, and the Medical Monitor.

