6. STUDY OBJECTIVES AND ENDPOINTS

6.1. Primary Objectives and Endpoints

Primary Objectives	Study Endpoints
Phase 1	

 • To assess the safety and tolerability of TP-0184 • To determine the maximum tolerated dose (MTD) or maximum administered dose (MAD) and recommended dose for the future expansion arms of TP-0184 in the Phase 2 part of the study 	Assessment of dose limiting toxicities (DLTs), treatment-emergent adverse events (TEAEs); type, frequency and severity of AEs and relationship of AEs to TP-0184, TP-0184 dose interruptions and dose reductions
Phase 2	
To determine the effect of TP-0184 on the treatment and the hematologic improvement of anemia in terms of hemoglobin increase, reduction in RBC transfusions and Transfusion-Free \geq 8 weeks	
Response rate based on composite response criteria:
 
Hemoglobin increase \geq 1.5 g/dL maintained for a consecutive period of 8 weeks with no transfusions
 
OR
 
Reduction in units of \geq 4 RBC transfusions / 8 weeks (consecutive) compared with the pretreatment transfusion number in previous 8 weeks
 
OR
 
Patients who are RBC transfusion-free over any consecutive 8-week (56-day) period

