8.3.1. Reasons for Treatment Discontinuation

A patient may be discontinued from TP-0184 treatment for any of the following reasons:

- In Phase 1, patient experiences a DLT during Cycle 1
- Failure to achieve a hematologic response. Patients not demonstrating evidence of hematologic response after the first 6 cycles (24 weeks) of treatment will be considered for treatment discontinuation, although with permission of the Medical Monitor and Investigator, TP-0184 study treatment may continue if clinically indicated and provided there is no evidence of Grade 4 toxicity.
- Grade 4 toxicity not responding to supportive measures and without a response to treatment
- The occurrence of any other AE, concurrent illness or laboratory abnormality which, in the opinion of the Investigator, warrants treatment discontinuation
- Patient noncompliance, defined as refusal or inability to adhere to the study schedule
- At the request of the patient, Investigator, SDP Oncology, or regulatory authority
- Patient is lost to follow-up
- Patient becomes pregnant while on study
- Patient begins another treatment for their disease
- Patient death
- Patient withdrawal of consent.

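### The primary response has no latest date by which it must occur, so opportunity to respond varies between patients and between looks while the 5% and 20% thresholds stay fixed

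*Protocol*

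**What the plan says.** Protocol 13.1.9.1.2.1 defines the rate as "the proportion of patients who achieves response according to the composite endpoint criteria for a consecutive period of 8 weeks" and refers to Appendix 1, which lists the three arms per 8 weeks without an anchor or a latest date. In 6.1 the transfusion-free arm reads "Patients who are RBC transfusion-free over any consecutive 8-week (56-day) period". The hemoglobin and 4-unit arms ask for a consecutive 8 weeks but are not tied to any calendar period either.

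Treatment is expected to last 24 weeks, with no maximum. The synopsis says that "patients may continue to receive TP-0184 in the absence of MDS disease progression or until loss of hematological response or unacceptable toxicity". Section 8.3.1 has patients without hematologic response after six cycles considered for discontinuation, but with permission "TP-0184 study treatment may continue if clinically indicated and provided there is no evidence of Grade 4 toxicity". In Table 6, transfusion data are collected until 30 days after the last dose or the end-of-treatment visit, whichever is later, so the observation period follows treatment length.

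Section 13.1.5 admits a patient to the efficacy evaluable set (EAS) with baseline data, one dose and one post-baseline response assessment under the composite criteria. Section 13.1.9 adds: "Bayesian posterior probability of response rate will be estimated continuously", starting from 10 evaluable patients. SAP section 1.2 repeats the endpoint, and the SAP supplies no window rule.

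**The concern.** A response that counts if it is ever met has a rate that depends on how long patients are watched. Here that length is neither fixed nor equal. It varies with how long each patient stays on treatment, and it is shorter at an interim look than at the final one. The futility rule (rate at or below 5%), the early efficacy rule and the final success rule (rate at or above 20%) all treat it as a single quantity.

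Two errors can follow, in opposite directions. A patient with stable transfusion need has more chances of a lucky 8 weeks the longer follow-up runs. At an interim look, a patient still inside the period in which response is possible may be entered as a failure. At stake is whether crossing a threshold says something about the drug or about the length of observation.

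**Working it through.** **Is there a figure to reproduce?** No. The protocol gives 10 to 60 patients for Phase 2 without a derivation, a prior, an error rate or an assumed chance response rate. The transfusion patterns and priors below are therefore assumptions, shown as ranges.

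**Step 1: direction.** Follow-up of T days contains T − 56 + 1 daily-start 56-day windows: 113 for 168 days (24 weeks) and 281 for 336 days (48 weeks). A patient who qualifies by week 24 has also qualified by week 48, so the probability cannot fall as T grows. This needs no assumption.

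**Step 2: size for the transfusion-free arm.** Assume no drug effect and transfusion visits at a stable mean rate λ per 8 weeks. Gaps between visits are gamma distributed with mean 56/λ days and shape k; k = 1 is fully irregular (Poisson) and larger k is more regular. Low burden in inclusion criterion 5 is fewer than 4 units in 8 weeks; visits per 8 weeks are not given. The table shows the simulated chance of at least one 56-day free run, if every patient stayed on:

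| λ | k | week 8 | week 24 | week 48 |
|---|---|---|---|---|
| 2 | 1 | 13.5% | 60.3% | 88.3% |
| 2 | 4 | 1.5% | 17.8% | 37.7% |
| 2 | 8 | <1% | about 4% | about 10% |
| 3 | 1 | 4.9% | 33.1% | 61.0% |
| 3 | 4 | 0.1% | 1.4% | 3.5% |

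Check for k = 1 against closed forms: exp(−2) = 13.5% at week 8, and exp(−2)(1 + 2) = 40.6% at week 16, as simulated. At one visit per 8 weeks the week-24 chance is higher still, 84-90% for k = 4 to 1.

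**Step 3: who is exposed after week 24.** Patients who stay on because they responded are already counted. If a share c of non-responders continues, the week-48 chance is P24 + c(P48 − P24). With c = 20% (assumed):
- λ = 2, k = 4: 17.8 + 0.2 × (37.7 − 17.8) = 21.8%
- λ = 2, k = 1: 60.3 + 0.2 × (88.3 − 60.3) = 65.9%

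**Step 4: link to the success rule.** Under an assumed Beta(1,1) or Beta(0.5,0.5) prior, Pr(θ ≥ 0.20) > 0.50 at N = 60 needs 12 responders. Under Beta(0.2,0.8) or Beta(0.05,0.95) it needs 13. If all 60 patients had the chance rates above, the probability of at least 12 at weeks 8 / 24 / 48 would be about 0 / 0.99 / 1.00 for λ = 3, k = 1; about 0 / 0.38 / 1.00 for λ = 2, k = 4; and about 0 throughout for λ = 3, k = 4. The week-48 values again assume that everyone stays on.

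**Step 5: interim maturity.** Among patients who would qualify by chance within 24 weeks (k = 1), the share not yet qualified at week t is 1 − P(t)/P(24). For λ = 2 this is 1 − 13.6/60.4 = 78% at week 8, 1 − 27.0/60.4 = 55% at week 12 and 1 − 40.7/60.4 = 33% at week 16. For λ = 4 it is 89%, 66% and 44%.

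**Step 6: can immaturity alone trigger futility?** With no responders among n and a Beta(1,1) prior, Pr(θ ≤ 0.05) = 1 − 0.95^(n+1). This is 0.43 at n = 10 and first exceeds 0.90 at n = 44. Under Beta(0.5,0.5) the first such n is 27. Under Beta(0.05,0.95) the rule is already met at n = 10 (0.97). The answer turns on a prior that the protocol does not state.

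**The case against.** The strongest reply is that the plan limits the problem in practice. Non-responders are reviewed at week 24, and continuation is otherwise tied to response, so few patients gain extra windows. That stands as a limit on size: Step 3 gives a rise of about 4 to 6 percentage points by week 48 if one non-responder in five continues. It does not close the endpoint, because the review is discretionary and concerns treatment, not when a response counts.

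A reader might infer that follow-up length would greatly inflate the final rate. The documents do not support that. They give neither the regularity of transfusions nor the share of non-responders who would continue, and with regular visits the chance is near nil. Most of the chance response also falls before week 24, where a cut-off leaves it untouched.

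On the interim looks, a reader might infer that pending patients are certainly scored as failures, or that futility would be declared wrongly. Neither is established. The EAS requires an assessment under the composite criteria, which may already imply one complete 8-week period, and section 13.1.6 treats missing data as missing. Both interim rules are also permissive. What stands is that no text defines when an outcome is mature, and that one complete 8-week period would not make a non-response final.

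Finally, only the transfusion-free arm says that any such period counts. The other two arms merely lack an anchor.

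**Conclusion.** The concern holds as a gap in the endpoint definition. There is no assessment cut-off and no maturity rule for monitoring, so fixed thresholds are applied to a rate that depends on unequal follow-up. The direction is certain.

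The size is not. For low-burden patients with two to three visits per 8 weeks and no drug effect, the chance of a 56-day free run is near 0% to about 60% by week 24, and near 0% to about 88% by week 48 if all stayed on. Those ranges rest on a stable transfusion rate and on assumed spacing from regular to fully irregular. Growth after week 24 reaches only the non-responders who continue.

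A cut-off would make patients and looks comparable. It would not bring the chance rate below 20% at low baseline need, so that target needs separate justification. No reported rate is affected: SAP section 2 records termination after two patients, with listings only. The point matters for any design that reuses this endpoint.

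**What to change.** In protocol 6.1, 13.1.9.1.2.1 and Appendix 1, state that the qualifying 8-week window (12-week for the secondary rate) must lie wholly within Weeks 1-24 from first dose. Report later responses descriptively. Do not let dose holds directed by the protocol disqualify a window: Table 5 in section 7.4 delays dosing on high hemoglobin, so an unqualified on-drug condition could exclude strong responders.

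In 13.1.3 and 13.1.9, include patients in the posterior in enrollment order, each once the 24-week window is complete or the patient has stopped earlier. Early responders are then not counted ahead of pending peers.

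The change is wording only and needs no new data. Its costs are that responses after week 24 no longer count toward the primary rate and that monitoring is slower. If patients now enter at week 8, the delay is up to 24 − 8 = 16 weeks each, and longer if they enter sooner. The accrual rate is not given, so how many patients would be enrolled during that wait cannot be worked out from the documents.
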